## 2.2 SCREENING EVALUATION

- 2.2.1 Any time prior to starting the therapeutic regimen:
  - a. HLA-Typing
  - b. Review of most recent cervical cytology and HPV testing. Cervical cytology testing will be performed if clinically indicated.
  - c. If a pathology report confirming vulvar HSIL is not available, if available results are unclear, or there is a lack of necessary information in the available results, a vulvar biopsy will be performed to confirm diagnosis.
  - d. Cervical high-risk HPV testing
  - e. Venous assessment (as per apheresis clinic policy)
  - f. One 10 mL tube of blood will be collected for the optional ddPCR-based research blood test.

2.2.2 Within 4 weeks prior to starting the therapy unless otherwise indicated:

- a. Complete history and physical examination, noting in detail the exact size and location of all lesions. (Note: Patient history may be obtained within 8 weeks prior to starting therapy.)
- b. Chest x-ray
- c. EKG
- d. Cardiac stress test for patients over the age of 50.
- e. HIV antibody titer, HbsAG determination, and anti-HCV antibody. (Note: may be performed within 3 months of therapy start date).
- f. Past medical history including family history, social history, allergies, and current medications.

2.2.3 Within 14 days prior to starting the therapy:

- a. Chem 20 equivalent: (Sodium (Na), Potassium (K), Chloride (Cl), Total CO2 (Bicarbonate), Creatinine, Glucose, Urea nitrogen (BUN), Albumin, Calcium total, Magnesium total (Mg), Inorganic Phosphorus, Alkaline Phosphatase, ALT/GPT, AST/GOT, Total Bilirubin, Direct Bilirubin, LD, Total Protein, Total CK, Uric Acid).
- b. Thyroid Panel
- c. CBC with differential and TBNK
- d. PT/PTT

2.2.4 Within 7 days prior to starting the therapy regimen:

- a. Beta-HCG pregnancy test (serum or urine) on all women of child-bearing potential
- b. ECOG performance status of 0 or 1

## **2.3 REGISTRATION PROCEDURES**

Registration will be a two-part process as patients are screened on this protocol. Authorized staff must register an eligible candidate with NCI Central Registration Office (CRO) within 24 hours of signing consent. To initially register a subject after the participant has signed the consent, complete the top portion of the registration Eligibility Checklist from the website (<http://home.ccr.cancer.gov/intra/eligibility/welcome.htm>) indicating that the patient is being registered for screening and send via encrypted email to: NCI Central Registration Office [[contact]](mailto:[contact]). Once eligibility is confirmed after completion of screening studies, complete the remainder of the form which is the eligibility checklist, indicating that the patient is being registered for treatment and email the completed registration checklist to the CRO at NCI Central Registration Office [[contact]](mailto:[contact]). After confirmation of eligibility at Central Registration Office, CRO staff will call pharmacy to advise them of the acceptance of the patient on the protocol prior to the release of any investigational agents. Verification of Registration will be forwarded electronically via e-mail to the research team. A recorder is available during non-working hours.

Subjects that do not meet screening criteria should be removed from the study following the procedure in section **3.6.3**.

2.3.1 Treatment Assignment and Randomization/Stratification Procedures for registration purposes only

**Cohorts**

Number	Name	Description
1	Cohort 1	Patients with HPV 16 positive vulvar HSIL enrolled to determine the MTD
2	Cohort 2	Patients with HPV 16 positive vulvar HSIL enrolled after MTD is determined

**Arms**

Number	Name	Description
1	Arm 1	Patients will undergo leukapheresis, then treatment with E6 TCR cells (at escalating doses) + aldesleukin
2	Arm 2	Patients will undergo leukapheresis, then treatment with E6 TCR cells (at the MTD) + aldesleukin

**Stratifications**

Not applicable to this protocol.

**Randomization and Arm Assignment**

This is not a randomized study. Patients in Cohort 1 will be directly assigned to Arm 1. Patients in Cohort 2 will be directly assigned to Arm 2.

**2.4 BASELINE PROCEDURES**

[figure not shown]
- a. Baseline photographs and optional biopsies of HSIL lesions to be performed under local anesthetic in the clinic within 8 weeks prior to therapy. Patients will be required to sign a separate consent for all biopsies conducted during the study. Refer to Section 5.4 for guidelines for handling specimens.
- b. Peripheral blood lymphocytes (PBLs), plasma, and serum collected at time of baseline biopsy. As noted in 5.1.3, Biopsies will not be performed if they are not technically feasible, if they will interfere with response assessment, or if a patient declines consent.
- c. Replication Competent Retrovirus (RCR) testing.
- d. Leukapheresis as described in section 3.1.2.

### **3 STUDY IMPLEMENTATION**

#### **3.1 STUDY DESIGN**

This is a phase I clinical trial with a 3+3 dose escalation design.

3.1.1 Protocol schema

### 3.1.2 Leukapheresis

The patient will undergo a 10-15 liter leukapheresis (generally, 12 liters will be processed to target yield of  $6-10 \times 10^9$  lymphocytes) in the Department of Transfusion Medicine (DTM) Dowling Apheresis Clinic according to DTM standard operating procedures. The procedure requires dual venous access, and takes approximately 3-4 hours to complete. A central line will be placed if peripheral venous access is not sufficient. The leukapheresis collection will be obtained at least 21 days prior to the cell infusion. Leukapheresis material that is not required for clinical use will be retained and cryopreserved in 10 vials at  $100 \times 10^6$  cells per vial with remaining cells stored at  $300 \times 10^6$  cells per vial for research and banked on protocol 16-C-0061 (ETIB Tissue Procurement Protocol).

### 3.1.3 E6 TCR T cell preparation

After cells are obtained by apheresis, further cell processing to generate E6 TCR cells will occur in the DTM according to standard operating procedures and the E6 TCR investigational new drug application. E6 TCR cells can be produced in approximately 21 to 27 days. Cell products may be cryopreserved during production to accommodate patient treatment schedules. Either freshly-collected cells or cryopreserved cells can be used to initiate the cell-preparation process. Peripheral blood mononuclear cells (PBMC) will be isolated. Sufficient cells for three complete cell productions (2-3 vials at  $3-4.5 \times 10^9$  cells/vial) will be retained in the DTM; the remaining cells will first be frozen in 10 vials at  $100 \times 10^6$  cells per vial with excess frozen at  $300 \times 10^6$  cells/vial. Cells will be frozen in the DTM and then transferred to ETIB the following day. Contacts in the ETIB preclinical core are [name] and [name] [contact]).

Before infusion, the percentage of T cells expressing the E6 TCR will be determined by flow cytometry. Successful TCR gene transfer will be defined as greater than 20% TCR positive cells. In addition to flow cytometry, further testing of the cells will take place prior to infusion to evaluate for microbial contamination, replication-competent retroviruses, and viability. Details of this testing can be found in the appropriate DTM SOPs. Any remaining pretreatment PBMC collected on this protocol and cryopreserved as described in Section 3.1.2 will be transferred from the Department of Transfusion Medicine to the Principal Investigator of this protocol for storage in the ETIB preclinical core and possible use in research and banked according to protocol 16-C-0061 (ETIB Tissue Procurement Protocol).

### 3.1.4 Treatment Phase

E6 TCR T cells will be infused while the patient is admitted to the hospital on treatment day 0. A central line catheter may be placed for cell infusion. The day after cell infusion, patients will receive aldesleukin 720,000 IU/kg IV q 12 hours x up to 2 doses. The second dose of aldesleukin will not be given if a patient develops any of the following: 1) hypotension or oliguria that require fluid boluses, 2) mental status changes, 3) hypoxia that requires supplemental oxygen, 4) diarrhea or nausea that are not controlled with symptomatic therapy. The second dose of aldesleukin may also be held for any safety concern at the discretion of the treating physician, and will not be given if a grade 3 or higher AE occurs following the first dose.

The patient will remain an inpatient for aldesleukin administration. Patients also will be observed overnight as inpatients following aldesleukin administration, and will not be discharged until cleared by the treating physician. Patients will receive one course of treatment.

### 3.1.5 Dose Limiting Toxicities (DLTs)

All treatment related Grade 3 and greater AEs occurring within 30 days of the cell infusion will be considered DLTs with the exception of the following expected transient effects of aldesleukin.

- Grade 3 fever or chills responsive to symptomatic treatment that resolve to  $\leq$  grade 2 in 48 hours.
- Grade 3 hypotension or oliguria responsive to  $\leq$  1.5L of IV fluid boluses in 24 hours that resolves to  $\leq$  grade 2 in 48 hours.
- Grade 3 dyspnea/hypoxia that improves to  $\leq$  grade 2 or less with supplemental oxygen and resolves to  $\leq$  grade 2 without supplemental oxygen in 48 hours.
- Grade 3 creatinine or electrolyte abnormalities that resolve to  $\leq$  grade 2 in 48 hours.
- Grade 3 or higher white blood cell count decreased and/or lymphocyte count decreased that resolves to  $\leq$  grade 2 in 72 hours.

Further outline of expected AEs with aldesleukin and their management is included in [Appendix B](#) and [Appendix C](#).

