### 13.3 APPENDIX C: EXPECTED ALDESLEUKIN TOXICITIES AND THEIR MANAGEMENT

Toxicity	Grade	Supportive Medications	Considered DLT*
Chills	3	IV Meperidine 25-50mg IV q1hr, prn	No
Fever	3	Acetaminophen 650mg po q4hr; Indomethacin 50-75mg po q8h	No
Pruritus	3	Hydroxyzine HCl 10-20mg po q6h, prn; Diphenhydramine HCl 25-50mg po q4h prn	No
Nausea/Vomiting/Anorexia	3	Ondansetron 10mg IV q8hr prn, Granisetron 0.01 mg/kg IV qday prn, Droperidol 1mg IV a4-6h prn; Prochlorperazine 25mg PR prn or 10mg IV q6hr prn	No
Diarrhea	3	Loperamide 2mg po q3h prn; Diphenoxylate HCl 2.5mg and Atropine sulfate 25mcg po q3h prn; Codeine sulfate 30-60mg po q4h prn	If uncontrolled after 48h despite all supportive measures
Malaise	3 or 4	Bedrest	If other toxicities occur simultaneously
Hyperbilirubinemia	3 or 4	Observation	Yes
Anemia	3 or 4	Transfusion with PRBCs	Yes
Thrombocytopenia	3 or 4	Transfusion with platelets	Yes
Edema/Weight gain	3	Diuretics prn	No
Hypotension	3	Fluid resuscitation, Vasopressor support	No, unless requires more than 1.5L/24 hours of bolus IV fluids or vasopressor support
Dyspnea	3 or 4	Oxygen or ventilator support	If requires more than nasal cannula oxygen support or requires oxygen for greater than 48 hours after last dose

Toxicity	Grade	Supportive Medications	Considered DLT*
Oliguria	3 or 4	Fluid boluses	If requires more than 1.5L/24 hours of bolus IV fluids
Increased Creatinine	3 or 4	Observation	If grade 3 lasts more than 48 hours or for any grade 4.
Renal Failure	3 or 4	Dialysis/CVVH	Yes
Pleural Effusion	3	Thoracentesis	Yes
Bowel Perforation	3	Surgical intervention	Yes
Confusion	3	Observation	Yes
Somnolence	3 or 4	Intubation for airway protection	Yes
Arrhythmia	3	Correction of fluid and electrolyte imbalances; chemical conversion or electrical conversion therapy	Yes
Elevated Troponin Levels	3 or 4	Observation	Yes
Myocardial Infarction	4	Supportive care	Yes
Elevated Transaminases	3 or 4	Observation	Yes
Hyperbilirubinemia	3 or 4	Observation	Yes
Electrolyte Imbalances	3 or 4	Electrolyte replacement	If uncontrolled after 48 hours despite all supportive measures
Neutropenia	4	Observation	Yes

\*Unless the toxicity is not reversed within 24 hours of last aldesleukin, in which case all AEs are considered DLTs.

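### Section 3.1.5 and the Appendix C Considered DLT column score some of the same aldesleukin events differently, and nothing says which governs

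*Combined protocol and SAP*

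**What the plan says.** Section 3.1.5 classes all treatment-related grade 3 or higher adverse events in the 30 days after infusion as DLTs, "with the exception of the following expected transient effects of aldesleukin". The five exempt groups are fever/chills, hypotension/oliguria, dyspnea/hypoxia, creatinine/electrolytes, and white cell/lymphocyte decreases. Each must resolve to grade 2 or less, within 48 hours for the first four and 72 hours for the last. Only the white cell/lymphocyte exemption goes above grade 3. For dyspnea the condition is resolution to "grade 2 without supplemental oxygen in 48 hours". The section then says: "Further outline of expected AEs with aldesleukin and their management is included in" Appendices B and C.

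Appendix C (section 13.3) goes beyond management, because it has a Considered DLT column. Grade 3 pruritus, nausea/vomiting/anorexia and edema/weight gain are scored No. Grade 3 diarrhea is a DLT "If uncontrolled after 48h despite all supportive measures". Grade 3 or 4 malaise is a DLT "If other toxicities occur simultaneously". Grade 3 or 4 dyspnea is a DLT "If requires more than nasal cannula oxygen support or requires oxygen for greater than 48 hours after last dose". A footnote on the column header reads "Unless the toxicity is not reversed within 24 hours of last aldesleukin, in which case all AEs are considered DLTs".

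Neither section 3.1.5, 3.1.6, 3.1.7, 8 or 11.1.6 nor the appendix says which text prevails.

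**The concern.** The DLT is the event behind the primary objective. Under section 3.1.6, two patients with DLTs stop the study at dose level -1 or end treatment at dose level 1. Rule 4 of section 3.1.7 lists two DLTs at dose level 1 as a condition for halting. The MTD then sets the dose for six more patients (section 8), and the two levels differ tenfold (0.7 × 10^10 against 0.7 × 10^11 cells).

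With one undisputed DLT at a level, a single disputed patient changes the outcome; with none, two do. The disputed events are foreseeable: section 11.1.6 names diarrhea, nausea, vomiting, anorexia and skin changes among the grade 3 toxicities common with aldesleukin. If the choice of text is left until events occur, the same patients could be scored either to stop or to escalate.

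**Working it through.** **Step 1. The two texts side by side.** All events are treatment-related and within 30 days. *Reversed* is not defined; here it is read leniently as back to grade 2 or less.

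| Event | Section 3.1.5 | Appendix C |
|---|---|---|
| Grade 3 pruritus, nausea/vomiting/anorexia or edema/weight gain, reversed within 24 h of last dose | DLT (not on the list) | Not a DLT |
| Grade 3 diarrhea, controlled and reversed within 24 h of last dose | DLT | Not a DLT |
| Grade 3–4 malaise alone, reversed within 24 h of last dose | DLT | Not a DLT |
| Grade 4 electrolytes, oliguria or dyspnea meeting the row's condition, reversed within 24 h of last dose | DLT (exemption stops at grade 3) | Not a DLT |
| Grade 3 fever starting at the last dose, grade 2 by 36 h | Exempt | DLT (footnote) |
| Grade 3 dyspnea needing more than nasal cannula, improving on oxygen and resolved off it within 48 h | Exempt | DLT (dyspnea row) |

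The first four rows are type A (DLT only under 3.1.5). The last two are type C (DLT only under Appendix C). White cell and lymphocyte decreases have no Appendix C row, so they conflict only if the footnote's reference to all AEs reaches them. Other rows agree: the 1.5 L fluid limit for grade 3 hypotension, and bilirubin, transaminases, confusion and arrhythmia as DLTs.

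**Step 2. The clocks.** Section 3.1.5 gives no start for its windows; the footnote runs from the last aldesleukin dose. If the 48 hours run from onset, an otherwise exempt event that starts t hours after the last dose is scored differently when it lasts between 24 − t and 48 hours: 24–48 h at t = 0, 18–48 h at t = 6, 12–48 h at t = 12.

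**Step 3. The plan's own numbers.** 2 levels × 6 = 12 patients to find the MTD, and 12 + 6 = 18 in all. Both match section 8 and do not depend on the definition used.

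**Step 4. Effect on the 3+3, one direction only.** The rates are assumptions. Let b be the undisputed DLT rate and q the rate of type A events among the other patients, the same at both levels. Appendix C gives p = b; section 3.1.5 gives p = b + (1 − b)q.

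- P(pass dose level -1) = (1 − p)³ + 3p(1 − p)⁵
- P(at most 1 of 6 at dose level 1) = (1 − p)⁶ + 6p(1 − p)⁵
- P(dose level 1 is the MTD) = the product

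For b = 0.10, q = 0: 0.906 × 0.886 = 0.803. For b = 0.10, q = 0.05: p = 0.145, and 0.824 × 0.788 = 0.649.

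| b | q | p | P(stop at dose level -1) | P(dose level 1 is MTD) |
|---|---|---|---|---|
| 0.05 | 0 | 0.050 | 0.027 | 0.942 |
| 0.05 | 0.05 | 0.098 | 0.090 | 0.811 |
| 0.10 | 0 | 0.100 | 0.094 | 0.803 |
| 0.10 | 0.02 | 0.118 | 0.125 | 0.743 |
| 0.10 | 0.05 | 0.145 | 0.176 | 0.649 |
| 0.10 | 0.10 | 0.190 | 0.270 | 0.496 |
| 0.20 | 0 | 0.200 | 0.291 | 0.464 |
| 0.20 | 0.05 | 0.240 | 0.379 | 0.347 |

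**Step 5. Both directions.** With b = 0.10, I enumerated six potential patients per level and scored each set by both texts. With types A and C mutually exclusive at 5% each, a patient is a DLT under both texts with probability 0.10, under one text only with probability 0.90 × 0.05 = 0.045 for each type, and under neither with probability 0.81.

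| Type A / type C | MTD = dose level 1: 3.1.5 | MTD = dose level 1: Appendix C | Opposite verdicts | Opposite, types independent |
|---|---|---|---|---|
| 1% / 1% | 0.773 | 0.773 | 0.056 | 0.056 |
| 2% / 2% | 0.743 | 0.743 | 0.108 | 0.106 |
| 5% / 5% | 0.649 | 0.649 | 0.237 | 0.228 |
| 10% / 5% | 0.496 | 0.649 | 0.329 | 0.315 |

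Equal averages can therefore hide frequent disagreement about the same patients.

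**The case against.** The best defense is that 3.1.5 plainly governs: it is the titled definition, it is worded as a rule with a closed list, and it introduces the appendices as an outline of events and management. That is a strong inference, but it is not stated. The appendix column and its footnote classify DLTs, and 3.1.5 itself sends the reader there. Even if 3.1.5 governs, its windows still lack a start.

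Exposure may also be low. Aldesleukin is capped at two doses, which section 1.2.5 describes as well tolerated. Section 3.1.4 withholds the second dose after any grade 3 event. Type A events are disputed only if they reverse within 24 hours of the last dose; otherwise the footnote makes them DLTs too. These points stand, and they argue for disputed rates at the lower end of the tables. They do not remove the conflict: the first dose alone can produce a disputed event, and when the second is withheld the first becomes the last dose that starts the 24-hour clock.

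One team makes the dose decisions (section 7.5.1), so one text might be applied throughout. It could still be the unintended one.

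Finally, the footnote may be meant only for rows scored No. On that reading it does not override Appendix C's own 48-hour rows (diarrhea, dyspnea, creatinine, electrolytes). The reading is possible, although the asterisk sits on the column header. The fever and chills conflict remains either way.

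**Conclusion.** The concern holds. The protocol contains two scoring rules for the event that decides stopping, escalation and the MTD. They give opposite answers in both directions for identifiable events, and no text sets an order of precedence. This follows from the wording alone and needs no assumed rates.

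The size is unknown: the documents give no grade 3 rates for two-dose aldesleukin, and the Appendix B percentages are ungraded. Under the assumed rates, a 5% one-directional disputed rate lowers the chance that dose level 1 becomes the MTD by 12 to 15 percentage points. Opposite verdicts on the same patients range from about 6% of trials (1% each way) to 33% (10% and 5%). These are illustrations, not bounds. It should be corrected before DLTs are scored.

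**What to change.** State in section 3.1.5 that it is the only DLT definition. Move into it any Appendix C exemption the sponsor wants to keep, such as grade 3 nausea/vomiting or diarrhea controlled within 48 hours, with the grade stated. Give each exception one window with a named start (onset or last aldesleukin dose), and define resolution once. Then delete the Considered DLT column and its footnote, or make them match.

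The sponsor must make a clinical decision on which exemptions to keep. Otherwise the cost is protocol wording: no extra patients, visits or tests, and the 3+3 rules and the 12 and 18 patient limits stay as they are.

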### 3.1.6 Dose Escalation

The protocol will follow a 3+3 phase 1 dose escalation design. Three patients will be treated initially on dose level -1. If 2 of these 3 patients experience DLTs, the study will be stopped. If none of the 3 patients experiences a DLT, enrollment can start on dose level 1. If 1 of the first 3 patients experiences a DLT on dose level -1, 3 more patients will be treated at that dose level. If a second patient of the 6 has a DLT, the study will be stopped; otherwise, accrual can proceed to dose level 1. On dose level 1, if 2 patients have DLTs at any time during the treatment of 6 patients, then treatment on dose level 1 will be stopped, and 3 additional patients will be accrued at dose level -1 to reach a total of 6, if only 3 were previously treated. The maximum tolerated dose is the highest dose at which a maximum of 1 of 6 patients has a DLT.

There will be a minimum of a 7-day delay in treatment between the patients and a minimum of a 14-day delay in treatment between cohorts.

The total number of E6 TCR T cells transferred for each cohort will be:

- **Dose level -1**  $0.7 \times 10^{10}$  transduced T cells
- **Dose level 1**  $0.7 \times 10^{11}$  transduced T cells

The cell dose administered will be in a range of +/- 30% of the target dose above. The frequency of transduced T cells will be determined by flow cytometry with anti-mouse TCR beta-chain antibody. The number of transduced cells to be administered will be determined by multiplying the frequency of transduced T cells by the total number of viable T cells. If fewer than the target number of cells are generated the patient will be treated but toxicity data from the patient will not be used in determining the MTD, and that patient will be replaced in the protocol enrollment.

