## 8 STATISTICAL CONSIDERATIONS

The primary objective of this phase I trial is to determine the safe dose level of E6 TCR T cells for the treatment of vulvar HSIL. Secondary objectives include an assessment of the clinical responses in subjects receiving this treatment and exploratory analyses of translational research endpoints.

This is a phase I trial with a standard 3+3 design and two dose levels. The maximum number of patients required to determine the MTD on this trial is 12. Six additional patients will be evaluated at the MTD, for a maximum intended enrollment of 18 patients. To allow for patients who enroll but are not evaluable for the primary endpoint and screen failures, up to 200 patients total may be enrolled.

The expected accrual rate is 10-15 patients per year. It should therefore take 1.25-2 years to complete accrual of patients.

The clinical responses in 12 patients tested at the MTD may be used in the design of a subsequent phase II trial.

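### With two dose levels, level 1 is named the MTD whenever it passes, although no higher dose is tested; the data would then show only that the highest dose given was tolerated

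*Combined protocol and SAP*

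**What the plan says.** Section 3.1.6 lists two dose levels, -1 and 1, and defines the target of the escalation: "The maximum tolerated dose is the highest dose at which a maximum of 1 of 6 patients has a DLT". It sets no condition that a higher dose was tried and failed. Level 1 fails under this rule: "if 2 patients have DLTs at any time during the treatment of 6 patients, then treatment on dose level 1 will be stopped". It therefore passes with 0 or 1 DLT.

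Section 8 repeats the structure, "This is a phase I trial with a standard 3+3 design and two dose levels", and gives the size: "The maximum number of patients required to determine the MTD on this trial is 12".

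The label is then used in three places:
- Cohort 2 in section 2.3.1 is described as "Patients with HPV 16 positive vulvar HSIL enrolled after MTD is determined", and Arm 2 is treated at that dose.
- Section 8 plans the expansion: "Six additional patients will be evaluated at the MTD, for a maximum intended enrollment of 18 patients".
- Section 8 also looks ahead: "The clinical responses in 12 patients tested at the MTD may be used in the design of a subsequent phase II trial".

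The documents have no provision for an MTD that is not reached. They also do not provide for reporting level 1 as a maximum administered or recommended dose.

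**The concern.** In a 3+3 design, an MTD has content as an upper limit when the next level up has been tried and found too toxic. Here level 1 is the top level, so when it passes there is no such observation. The rule still returns the same label, and it does so equally for 0 of 6 and 1 of 6.

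What is at stake is how the result is read. A phase II team told that level 1 is the MTD could take it that higher doses are not tolerable, and the trial would hold no data on that. The documents themselves treat the two ideas as distinct. Sections 1.2.3 and 1.2.6 report that in the earlier trial of these cells the maximum administered dose was declared the maximum tolerated dose, with no cell-related DLT in 12 patients. The current definition would repeat that step automatically.

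**Working it through.** **1. The plan's own figures.** Two levels × 6 patients = 12 to determine the MTD. 12 + 6 expansion patients = 18. At the chosen level, 6 + 6 = 12. All three agree with section 8.

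**2. What the definition returns on each path** (3.1.6):

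| Level -1 | Level 1 | Dose named MTD | Higher dose tested and failed? |
|---|---|---|---|
| 0/3 or 1/6 | 0/6 | level 1 | no |
| 0/3 or 1/6 | 1/6 | level 1 | no |
| at most 1/6 in total | 2 or more DLTs | level -1 | yes |
| 2 or more DLTs | any, or not opened | none | – |

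Only the third row brackets an MTD. The text does not say outright that six patients are treated at level 1 when the first three have no DLT. I infer it from the reference to six patients in the level 1 rule, the denominator in the definition and the total of 12.

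**3. How often each row arises.** The documents give no DLT rates. I assume true rates p at level -1 and q at level 1, with independent patients.

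P(level -1 passes) = (1−p)³ + 3p(1−p)² × (1−p)³

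P(level 1 has at most 1 of 6) = (1−q)⁶ + 6q(1−q)⁵

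- p = 5%, q = 10%: level -1 gives 0.857 + 0.135 × 0.857 = 0.973. Level 1 gives 0.531 + 0.354 = 0.886. Product: 0.862, or 86%.
- p = 10%, q = 20%: level -1 gives 0.729 + 0.243 × 0.729 = 0.906. Level 1 gives 0.262 + 0.393 = 0.655. Product: 0.594, or 59%.

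The bracketed path needs at most 1 of 6 at level -1 and failure at level 1:
- p = 5%, q = 10%: 0.967 × (1 − 0.886) = 0.11.
- p = 10%, q = 20%: 0.886 × (1 − 0.655) = 0.31.

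These two figures suppose that level -1 is filled to six as 3.1.6 describes. Section 3.1.7 also lists two DLTs at level 1 as a ground on which the study may be halted, which could only make this path rarer.

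**4. What a pass supports.** One-sided 95% exact (Clopper-Pearson) upper bounds on the DLT rate at level 1:
- 0/6: 1 − 0.05^(1/6) = 39%. For 1/6: 58%.
- If the six expansion patients add no DLT, 0/12: 1 − 0.05^(1/12) = 22%. For 1/12: 34%.

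Each bound describes the dose given. None of them concerns a higher dose.

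**The case against.** The strongest reply is that the protocol defines its term and applies it as defined. The rule is a common working definition for 3+3 trials, and under it an MTD is formally determined when level 1 passes. The two levels are stated openly, so a careful reader can see that nothing above level 1 was tried. All of that stands. It does not settle the matter, because the label is carried into Cohort 2, Arm 2 and a possible phase II design without the qualification, and the background sections already keep the two terms apart.

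Several stronger readings are tempting, and the documents do not support them:

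- A reader might infer that the primary conclusion fails. Section 8 words the objective as to "determine the safe dose level of E6 TCR T cells for the treatment of vulvar HSIL", which the design can address without an MTD.
- A reader might infer harm to patients or a wrong sample size. Escalation, stopping, doses and the totals of 12 and 18 are the same under either label. So are the clinical responses that phase II may use.
- A reader might take the bounds of 39% and 58% as the size of the problem. They reflect having six patients, would be the same for a properly bracketed dose, and leave out the expansion.
- A reader might compare level 1 with the MTD of 1.7 × 10^11 cells declared in the earlier trial (1.2.6). That section does not say whether the count is of total or transduced cells, so the comparison is not firm and I do not use it.

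**Conclusion.** The point holds as one of labelling and interpretation. Whenever level 1 has 0 or 1 DLT in 6, the plan will report an MTD that its data cannot bracket. The supported statement is that the highest dose administered was tolerated.

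On the assumed DLT rates, that outcome occurs in about 86% of trials (5% and 10%) or 59% (10% and 20%), against about 11% and 31% for the bracketed path. These percentages show how often the label would be applied without support. They do not measure a consequence, and they move with the assumed rates. The finding itself follows from the definition and the two levels, and depends on no assumed rate.

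**What to change.** **Section 3.1.6 and section 8.** State that if level 1 has at most 1 DLT in 6, it is reported as the highest dose administered and tolerated, MTD not reached. Give the DLT count and exact upper bound over all evaluable patients at that level, including the expansion patients. Reserve the term MTD for level -1 after level 1 has failed.

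**Section 2.3.1, Cohort 2 and Arm 2.** Make matching edits, for example: the MTD or, if not reached, the highest tolerated dose level. Without these, no MTD would be determined when level 1 passes, and the expansion would have no trigger. With them it opens at the same level as under the current plan. The references to the MTD in section 8, for the expansion and for phase II planning, should use the same phrase.

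**Cost.** A few sentences. No change to doses, escalation, stopping rules or patient numbers. The downside is a slightly less favourable label for the result.
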